13.3 Informed Consent Procedures

- a) Eligible patients may only be included in the study after providing written informed consent, or, if applicable, after such consent has been provided by a legally acceptable representative(s) of the patient. Verbal or electronic consent (eConsent) may be used where consistent with local regulations.
- b) Informed consent must be obtained before conducting any study-specific procedures (i.e., all procedures described in the protocol)


15. Appendices

1. Study Organization and Oversight

This study was initiated by independent scientists in the Critical Care Cardiology Trial Networks, TIMI Study Group, at Brigham and Women's Hospital and Harvard Medical School. The TIMI Study Group will act as the sponsor for the trial.

TIMI Principal Investigators

The Principal Investigators have overall responsibility for:

- a) Design and conduct of the study in collaboration with the Steering Committee;
- b) Preparation of the protocol and subsequent revisions;
- c) Development of the eCRF;
- d) Development of the statistical analysis plan;
- e) Interpretation of the final data and reporting of the study.

Steering Committee

The Steering Committee is responsible for:

- a) Reviewing and commenting on the final protocol and statistical analysis plans;
- b) Reviewing progress of the study and, if necessary, advising on protocol revisions;
- c) Reviewing study publications and substudy proposals;
- d) Reviewing external new studies that may be of relevance.

Data Monitoring Committee

The independent Data Monitoring Committee is responsible for:

- a) Reviewing unblinded data as per the DMC charter;
- b) Advising the Principal Investigators if, in its view, the data provide evidence that may warrant modification of the trial protocol or early termination for either efficacy or safety.

Clinical Events Committee

The Clinical Events Committee is responsible for independently reviewing, interpreting, and adjudicating potential endpoints that are experienced by the patients. (NB: The precise responsibilities and procedures applicable to the CEC will be detailed in the CEC Charter.)

2. Guidelines for Monitoring Coagulation Parameters

Treatment will be open-label and hospital-supplied by the institutional pharmacy per standard practice using local, standard formulations, concentrations and titration.

Unfractionated heparin (UFH) should be administered intravenously with an institution- or provider-determined nomogram targeting an aPTT of 1.5-2.5 times the control as per institutional therapeutic target for treatment of VTE. Similarly, if heparin-induced thrombocytopenia is confirmed or suspected, and a patient is transitioned to a direct thrombin inhibitor (bivalirudin or argatroban), these should be administered intravenously with an institution- or provider-determined nomogram targeting an aPTT of 1.5-2.5 times the control as per institutional therapeutic target for treatment of VTE. It is also acceptable

to use an institution- or provider-determined nomogram targeting an anti-Factor Xa level of 0.3-0.7 IU/ml for any of the intravenous FDAC regimens. Prothrombin time(PT)/international normalized ratio (INR) should be monitored daily, and fibrinogen level should be monitored at least every 3 days while the subject requires ICU level care.

3. Guidelines for Transitions in Randomized Treatment

The investigator may transition between acceptable regimens within the randomized treatment assignment as deemed appropriate clinically (e.g., transition from enoxaparin to subcutaneous heparin for standard-dose prophylactic anticoagulation in the setting of new or worsening renal failure). In addition, transitions to direct thrombin inhibitors are permitted if heparin-induced thrombocytopenia is confirmed or suspected.

Acceptable alternative regimens for FDAC include:

- Bivalirudin administered intravenously with a nomogram targeting an aPTT of 1.5-2.5 times the control as per institutional therapeutic target for treatment of VTE
- Argatroban administered intravenously with a nomogram targeting an aPTT of 1.5-2.5 times the control as per institutional therapeutic target for treatment of VTE
- Fondaparinux administered subcutaneously once daily with dosing according to weight (<50 kg: 5 mg once daily; 50-100 kg: 7.5 mg once daily; >100 kg: 10 mg once daily)

Review with the Central Coordinating Center any modifications in dosing in your hospital guidelines for patients at the extremes of body weight. Equivalent dosing of alternative LMWH preparations is detailed in the Manual of Site Operations.

Acceptable alternative regimens for SDPAC include:

- Fondaparinux administered subcutaneously 2.5 mg once daily

After a patient is transferred out of the ICU, transitions to oral anticoagulation are also permitted.

Acceptable alternative regimens for FDAC outside of the ICU and prior to hospital discharge include:

- Apixaban administered orally 5 mg twice daily
- Rivaroxaban administered orally 20 mg once daily
- Edoxaban administered orally 60 mg once daily (if body weight >60 kg) or 30 mg once daily (if body weight <60 kg or CrCl 30-50 ml/min)
- Dabigatran 150mg orally twice daily
- Warfarin with a target International Normalized Ratio (INR) of 2-3

Note that, in general, NOACs should not be used in patients with significant renal dysfunction or with Child-Pugh B/C hepatic dysfunction. Refer to package insert recommendations for DVT/PE treatment dosing for each individual NOAC for patients with renal or hepatic dysfunction.

The decision to transition therapy is left to the discretion of the investigator. Transitions in randomized treatments do not constitute a deviation in treatment strategy. All transitions in anticoagulant therapy will be recorded in the eCRF. The indications for antithrombotic therapy at the time of hospital discharge are determined by the managing clinician according to local standards of care.

4. Criteria for ICU-Level of Care

Patients are considered to have been admitted to an ICU if they were either admitted to a regular ICU room or if they were in a non-ICU room that is functioning as an ICU room to accommodate surge capacity. Non-ICU rooms are considered to be functioning as an ICU under any of the following conditions:

- The patient is being treated by an ICU team
- The patient is receiving advanced respiratory support (i.e, invasive mechanical ventilation, non-invasive positive pressure ventilation for respiratory insufficiency, or high flow nasal canula of at least 10L/min), vasopressors for at least 1 hour, continuous renal replacement therapy or mechanical circulatory support.

16. Changes to the Protocol

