 - e) International normalized ratio (INR) $>$ 1.9
4. History of heparin-induced thrombocytopenia
5. Ischemic stroke within the past 2 weeks
6. Pregnancy
7. Study staff or their family members
8. Any condition which in the investigator's assessment might increase the risk to the patient or decrease the chance of obtaining satisfactory data to achieve the objectives of the study
9. Subjects for whom further care is being forgone at the decision of the subject, family, and/or treating team ("comfort measures only")

Exclusion-based laboratory results are based on most recent values from within 2 days prior to randomization for platelet count and INR and within 3 days prior to randomization for fibrinogen.

Patients who meet the following criterion are excluded from the second randomization (antiplatelet therapy vs. no antiplatelet therapy):

1. Ongoing or planned antiplatelet therapy, including aspirin monotherapy

7. Study Intervention

7.1 Investigational Product Information:

Acceptable initial regimens for FDAC include the following:

- UFH administered intravenously with a nomogram targeting an aPTT of 1.5-2.5 times the control as per institutional therapeutic target for treatment of VTE
- Enoxaparin 1 mg/kg administered subcutaneously every 12 hours (if CrCl \geq 30 ml/min)

Acceptable initial regimens for SDPAC include the following:

- Enoxaparin 40 mg administered subcutaneously once daily (if CrCl \geq 30 ml/min)*
- Enoxaparin 30 mg administered subcutaneously once daily (if CrCl $<$ 30 ml/min)
- Heparin 5,000 units administered subcutaneous three times daily

**Enoxaparin 30-40 mg administered SC twice daily may also be considered if CrCl \geq 30 ml/min and BMI \geq 35 kg/m².*

Acceptable regimen for randomized antiplatelet therapy is:

- Clopidogrel 300 mg administered once orally on the day of randomization, followed by 75 mg administered once daily on subsequent days

7.2 Randomized Treatment Assignment: Randomization to FDAC versus SDPAC and AP therapy versus no AP therapy will be done via an Interactive Web-based Randomization System (IWRS). Treatment will be open-label and hospital-supplied by the institutional pharmacy per standard practice using local, standard formulations, concentrations and titration.

Randomization and study treatment initiation should be done as soon as possible following ICU admission or the requirement for ICU-level of care and no longer than 96 hours after meeting ICU-level criteria.

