7.3 Duration of Randomized Treatment: The study allocated regimen should be continued until hospital discharge (including after ICU discharge) or through 28 days post-randomization, whichever occurs first.

7.4 Transition in Randomized Treatment Assignment: The investigator may transition between acceptable regimens within the randomized treatment assignment as deemed appropriate clinically (e.g., transition from enoxaparin to subcutaneous heparin for SDPAC in the setting of new or worsening renal failure). Transitions to direct thrombin inhibitors, or fondaparinux are permitted if heparin-induced thrombocytopenia is confirmed or suspected. After a patient is transferred out of the ICU, transitions to oral anticoagulation are also permitted in the absence of significant renal or hepatic dysfunction (see Protocol Appendix for further details). Transitions in anticoagulant therapy will be recorded in the

eCRF. Refer to the Appendix for further guidelines regarding transitions in randomized treatment assignment including acceptable alternative regimens.

7.5 Blinding: Treatment will be open-label without blinding.

7.6 Concomitant Medications: All non-antithrombotic therapy is at the discretion of the patient's treating physicians. Non-study anticoagulant or antiplatelet therapy is not permitted while receiving the study allocated regimen unless there is a change in the patient's clinical status requiring an alternative regimen.

7.7 Discontinuation of Study Drug: Patients and healthcare providers may voluntarily discontinue study drug for any reason at any time. If adverse events occur that are believed to be due to study drug, or safety events occur that, in the opinion of the investigator, contraindicate further dosing of study drug, study drug may be temporarily interrupted or permanently discontinued. Whenever possible, restarting study drug should be encouraged, so long as the investigator judges that the potential benefit outweighs the risk. Situations that warrant temporary or permanent study drug discontinuation include:

- Active clinically significant bleeding
- Acute hemorrhagic or ischemic stroke at meaningful risk for hemorrhagic transformation
- Severe thrombocytopenia (platelet count <50,000)
- Evidence of overt disseminated intravascular coagulation (e.g. fibrinogen levels <150 mg/dl or INR >2.9 despite adequate vitamin K repletion). See Manual of Site Operations for guidelines to help discriminate DIC from sepsis induced coagulopathy.

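### Appendix 2 accepts an anti-Factor Xa target for every intravenous full-dose regimen, which as written includes two direct thrombin inhibitors

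*Combined protocol and SAP*

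**What the plan says.** Appendix 2 (Guidelines for Monitoring Coagulation Parameters) takes three steps on intravenous FDAC.

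1. For heparin: "Unfractionated heparin (UFH) should be administered intravenously with an institution- or provider-determined nomogram", with an aPTT target of 1.5-2.5 times control.
2. For patients with confirmed or suspected HIT who are "transitioned to a direct thrombin inhibitor (bivalirudin or argatroban), these should be administered intravenously with an institution- or provider-determined nomogram", the same aPTT target applies.
3. As an acceptable alternative, it allows a "nomogram targeting an anti-Factor Xa level of 0.3-0.7 IU/ml for any of the intravenous FDAC regimens".

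Appendix 3 (Guidelines for Transitions in Randomized Treatment) lists the two thrombin inhibitors as alternative FDAC regimens, each with an aPTT target: "Bivalirudin administered intravenously with a nomogram targeting an aPTT of 1.5-2.5 times the control" and "Argatroban administered intravenously with a nomogram targeting an aPTT of 1.5-2.5 times the control". The third alternative there is not intravenous: "Fondaparinux administered subcutaneously once daily with dosing according to weight".

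Section 7.4 says when these drugs may be used: "Transitions to direct thrombin inhibitors, or fondaparinux are permitted if heparin-induced thrombocytopenia is confirmed or suspected". Section 6 excludes patients with a "History of heparin-induced thrombocytopenia".

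**The concern.** Step 3 of Appendix 2 is a titration rule for full-dose anticoagulation in critically ill patients, and the primary safety outcome of the trial is fatal or life-threatening bleeding. Such a rule needs a laboratory measure that responds to the drug being titrated. For UFH the anti-Factor Xa option raises no difficulty here. For bivalirudin and argatroban, the class name that the protocol gives them says that they inhibit thrombin, so a Factor Xa measure cannot be relied on to show whether the dose is too low, right or too high.

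What is at stake is dose control in the few patients who need one of these drugs at a site that takes up the option. No estimate or test in the trial is at stake.

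**Working it through.** No arithmetic is needed. The check is which drugs the sentence reaches, and whether any other text narrows it.

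**Step 1. List the FDAC regimens by route.**

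| FDAC drug | Where named | Route | Protocol calls it a direct thrombin inhibitor in Appendix 2 | Covered by the anti-Factor Xa sentence |
|---|---|---|---|---|
| UFH | Section 7.1, Appendix 2 | intravenous | no | yes |
| Bivalirudin | Appendices 2 and 3 | intravenous | yes | yes |
| Argatroban | Appendices 2 and 3 | intravenous | yes | yes |
| Enoxaparin 1 mg/kg | Section 7.1 | subcutaneous | no | no |
| Fondaparinux | Appendix 3 | subcutaneous | no | no |
| Apixaban, rivaroxaban, edoxaban, dabigatran, warfarin | Appendix 3, after ICU transfer | oral | no | no |

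Appendix 3 also mentions other low-molecular-weight heparins, with dosing left to the Manual of Site Operations. It describes none of them as intravenous.

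Three drugs are intravenous, and two of the three are direct thrombin inhibitors.

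**Step 2. Test whether the sentence could mean UFH alone.** It speaks of regimens in the plural and applies to any of them. UFH is the only intravenous FDAC drug that is not a direct thrombin inhibitor. The sentence also comes directly after the one on bivalirudin and argatroban. A UFH-only reading does not fit the words.

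**Step 3. Look for a limit elsewhere.** Anti-Factor Xa is mentioned nowhere else in the documents, so no other section restricts it.

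**Step 4. Ask whether Appendix 3 restricts it by giving aPTT alone.** It does not. Section 7.1 also lists UFH with aPTT alone, and there the Appendix 2 alternative is plainly meant as an addition. By the same logic it adds to the Appendix 3 entries.

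**Step 5. Ask whether the target suits the drugs.** UFH: yes, on the protocol's own terms. Bivalirudin and argatroban: no. The documents do not say this outright. It follows from the class name they use, together with the general point that a Factor Xa measure does not gauge inhibition of thrombin.

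**The case against.** The case on the other side limits the reach of the error and deserves weight.

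- **The option is permissive.** Nobody is told to use it. The two places that name bivalirudin and argatroban individually both give the aPTT target.
- **Titration is local.** Sections 7.2 and 9 and the opening of Appendix 2 leave titration or monitoring to local practice, and the disputed sentence relies on a nomogram set by the institution or provider. Nothing in the documents suggests that any site has an anti-Factor Xa nomogram for a thrombin inhibitor.
- **Coagulation is still watched.** Appendix 2 requires INR daily, and fibrinogen at least every 3 days, during ICU-level care. Section 7.7 gives INR above 2.9 or fibrinogen below 150 mg/dl as examples of overt disseminated intravascular coagulation that warrants interruption or discontinuation. These checks do not replace titration of the drug, but they are a safeguard.
- **Few patients come within reach.** A patient must be allocated to FDAC, have confirmed or suspected HIT during the trial, be given an intravenous thrombin inhibitor and not fondaparinux, and be treated where the option is used.

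All four stand. They narrow the consequence but do not make the sentence correct.

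Three stronger readings are tempting, and the documents support none of them.

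- A reader might infer a number of patients at risk. The planned FDAC arm is 750/2 = 375, so each 1% switched is 3.75 patients. That is only an upper bound on those covered, because some would receive fondaparinux, and no HIT rate is given to say how many 1% steps apply.
- A reader might infer that patients would be overdosed. That would need a site to titrate one of these drugs by this level, which the documents do not show.
- A reader might add the synopsis line for enoxaparin 1 mg/kg, which lacks the creatinine clearance limit of 30 ml/min. Section 7.1 is operative and carries that limit. The omission is editorial and not part of this point.

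**Conclusion.** The point holds as an error of wording in a dosing guideline. As written, the anti-Factor Xa option covers three intravenous drugs and is unsuitable for two of them, bivalirudin and argatroban. No text in the documents narrows it.

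Its practical reach is small, for the reasons set out under the objection. No count of exposed or harmed patients is claimed, and sample size, power and analysis do not change. The correction is still worth making, because the sentence governs full-dose anticoagulation in ICU patients and the remedy is one phrase.

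The conclusion rests on two assumptions: that an anti-Factor Xa level does not gauge the effect of a direct thrombin inhibitor, which is inferred from the drug class, and that the Manual of Site Operations, which is not among the documents, does not already restrict the option to UFH. If the Manual does restrict it, the protocol text should still be brought into line.

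**What to change.** In Appendix 2, replace the closing words that extend the anti-Factor Xa option to all intravenous full-dose regimens with *intravenous UFH*. Leave the aPTT target of 1.5-2.5 times control for bivalirudin and argatroban as it stands in Appendices 2 and 3.

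The cost is one phrase at the next amendment and a short note to sites. Design, sample size and analysis need no change.

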16.1 Protocol Amendment 1 – October 28, 2020

- Acceptable initial regimens for standard dose prophylactic anticoagulation

To be consistent with accepted dose modifications for obesity, enoxaparin 40 mg SC twice daily is added as an alternative for individuals with CrCl \geq 30 ml/min and BMI \geq 35 kg/m².

- Inclusion criteria

- Given emerging new technology for high specificity testing, confirmation of SARS-CoV2 may include acceptable alternatives to SARS-CoV2 RT-PCR or SARS-CoV2 IgM antibodies
- To accommodate the range of turn-around times for SARS-CoV2 testing, the time window from ICU admission to randomization is increased from 72 hours to 96 hours.
- Clarification that ICU admission also includes patients requiring ICU-level care in other units. Criteria for ICU-level of care are defined in the Protocol Appendix.

- Exclusion criteria

- Clarification that study staff rather than any employee of the hospital system are excluded from participation in the study.
- For clarity, time windows for exclusions based on local laboratory results are added.

- Study procedures

- Review of laboratory results during screening added as an explicit procedure.
- To reduce the burden of testing when not needed for safety, the time period for performance of INR daily and fibrinogen every 3 days is modified to the duration of ICU-level care. Outside this time window, testing is according to local standard practice.
- To mitigate exposures to COVID-19, verbal or electronic consent (eConsent) may be used where consistent with local regulations.

- Acceptable alternative regimens for FDAC outside of the ICU and prior to hospital discharge

- Updated to include dabigatran and warfarin, both of which are acceptable anticoagulants.
- For consistency with standard practice, cautions for subjects with renal or hepatic dysfunction are updated to refer to individual package labeling.

- Correction of grammatical and typographic errors
